1.0 INTRODUCTION

Background:

Lymphatic mapping and axillary sentinel node biopsy has become a standard procedure for the surgical staging of patients with early stage breast cancer. It has been shown to be safe and accurate and limits significantly the need for traditional axillary dissection in many patients with early stage breast cancer. Traditionally, lymphatic mapping has involved the use of ^{99m}Tc -labeled radiotracer, or visible blue dye (methylene blue or isosulfan blue dye), or a combination of ^{99m}Tc -labeled radiotracer and visible blue dye. Sentinel nodes are defined as axillary lymph nodes in which there is the accumulation of one or more of these tracers or dyes.

The use of ^{99m}Tc -labeled radiotracer has a long history and is one of the more commonly used techniques of identifying sentinel nodes. However, the use of radiotracers has significant limitations including the requirement for nuclear licensing; the need to prepare, handle and dispose of nuclear material, patient inconvenience with painful injections typically occurring before surgery.

There is a growing body of literature supporting the role of indocyanine green (ICG) dye for lymphatic mapping in Europe and Japan. ICG is a fluorescent dye which can be detected using near infrared cameras. The use of ICG in conjunction with a near infrared camera offers many potential advantages over the use of other techniques including the ability to inject the material while the patient is under anesthesia in the operating room, the ability to use near infrared imaging to directly visualize lymphatic flow, and no special material handling is required. ICG is FDA approved for vascular fluorescence and liver function studies in humans.

ICG is a di-sulfonated heptamethine indocyanine with moderate optical properties, which emits ≈ 800 nm. There are many uses for ICG during image-guided surgery. After intravenous injection, it can be used for NIR angiography of blood vessels, identification of the extrahepatic bile ducts, and identification of liver metastases. After subcutaneous injection, ICG has been reported by numerous authors to be safely used for sentinel lymph node (SLN) mapping(1-5) and assessing lymphatic function.”(6)

ICG has been used for the last 50+ years as a visible dye (green for ICG). Thus, there is an unprecedented body of clinical data regarding their safety when used at millimolar concentrations.” (6) The use of ICG for lymphatic mapping in breast cancer patients has been demonstrated to be safe in numerous human studies performed in Asia and Europe (7-11). There is a recent retrospective case series report of using ICG for lymph node mapping in patients with melanoma from the Cleveland Clinic documenting its safety for in human use and lymphatic mapping (12).

A recent study from Europe has demonstrated high concordance between the number nodes identified with ICG and ^{99m}Tc -labeled radiotracer (11). There has been very limited work on the use of ICG for axillary lymph node mapping in humans in the United States, and no comparison studies of ICG with ^{99m}Tc -labeled radiotracer. The goal of the project is to confirm that axillary lymphatic mapping with ICG leads to a similar number of nodes being labeled as sentinel as lymphatic mapping with ^{99m}Tc -labeled radiotracer. Successful completion of this project would support the use of ^{99m}Tc -labeled radiotracer with ICG for LN mapping in early stage breast cancer patients.

2.0 OBJECTIVE

Hypothesis:

ICG is equivalent to ^{99m}Tc -labeled radiotracer for axillary lymphatic mapping in patients with early stage breast cancer in terms of the numbers of nodes identified as sentinel by each method being similar.

3.0 STUDY DESIGN

Methods:

Patients with a confirmed diagnosis of clinical stage 1 or 2 breast cancer who are undergoing breast cancer surgery with lumpectomy or mastectomy and planned axillary sentinel node biopsy procedure will be eligible for the study. Patients with cancer $> 3\text{cm}$, clinically positive nodes, prior surgery for breast cancer in the index breast, bilateral sentinel lymph node mapping, thyroid dysfunction, hypersensitivity to iodine, and hepatic or renal insufficiency will be excluded from the study.

- We plan to enroll approximately 130 adult female patients who will be identified in the breast clinic at Cleveland Clinic Main Campus.
- Informed consent will be obtained.
- Patient information will be collected from the medical record and entered in Redcap.

Patients will undergo lymphatic mapping with ^{99m}Tc sulfur colloid in accordance with routine clinical practice. Injections of ^{99m}Tc sulfur colloid will take place the afternoon prior to planned next morning surgery or on the morning of surgery. Patients will undergo lymphoscintigraphy in accordance with standard clinical practice.

Immediately prior to operation, after the induction of anesthesia in the operating room, up to 1cc of 0.5% ICG solution will be injected subdermally or intradermally close to, above the tumor, into the subareolar region or into the periareolar region after disinfection of the breast skin. ICG movement will be facilitated by manual massage and monitored with fluorescence imaging. ICG fluorescence will be elicited and detected by PDE camera (Hamamatsu Photonics, Hamamatsu, Japan) which has FDA 510(k) clearance to visualize ICG fluorescence in the humans for vascular imaging. The lymphatic drainage, made evident by the fluorescent dye, will be monitored in real time on a monitor. The fluorescence will be followed towards the axilla and time for the fluorescence to reach the axilla will be recorded. In accordance with standard practice, an incision will be made in the axilla. Fluorescent lymph nodes (ICG positive) will be localized and removed and sent for pathologic analysis as per standard surgical practice. Node removal will continue until no residual fluorescence is visible in the axilla. Excised nodes will be tested for radioactivity using a standard gamma-detecting probe and the counts per minute will be recorded. Finally, the axillary region will be inspected with the gamma probe to determine if there are any residual radioactive nodes. Residual sentinel nodes will be removed. With regard to radioactivity, sentinel nodes are defined as any node with at least 10% of the hottest nodal counts.

The following information will be collected for each removed node:

1. Fluorescence (yes/no)
2. Counts per minute
3. Pathologic status of node (no metastasis, isolated tumor cells, micrometastasis, macro-metastasis)

Also collected will be procedure related data including transit time to axilla from time of injection, size of tumor, location of tumor, tumor histology, breast size, patient age, BMI.

Consent:

All subjects for this study will be provided a consent form describing this study and providing sufficient information for subjects to make an informed decision about their participation in this study. The formal consent of a subject, using the IRB-approved consent form, will be obtained before that subject is submitted to any study procedure. Consent will be obtained by the study coordinator or investigator of the study in the breast clinic on Main Campus at Cleveland Clinic. Consent will be documented in the medical record.

Finance:

There are no additional costs to the patients. Mitaka USA will provide the PDE neo camera and ICG kit.

Funding Source:

CCF Breast Services Division

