7.0 STATISTICAL CONSIDERATIONS

Sample size:

The study will be designed to determine whether ICG based axillary sentinel lymph node biopsy yields a similar number of nodes as ^{99m}Tc sulfur colloid lymph node biopsy. While SLN identification using ^{99m}Tc sulfur colloid is a common technique, neither of the two methods used in this study can be assumed to identify the “correct” set of nodes as sentinel. Therefore, for the purposes of this study, the sentinel status of a node will be defined as being flagged as sentinel by either one or both of the ICG or ^{99m}Tc methods. By this definition, sentinel nodes identified by ^{99m}Tc but not ICG are an error by omission for the ICG method and nodes flagged by ICG but not ^{99m}Tc are an error by the ^{99m}Tc method.

Let A be the number of Tc-positive and ICG-positive SNs detected, B be the number of Tc-positive and ICG-negative SNs detected, and C be the number of Tc-negative and ICG-positive SNs detected. The total number (N) of SNs detected is therefore $N = (A + B + C)$; the proportion of SNs (P_{Tc}) detected by the Tc method is $(A + B)/N$; and the proportion of SNs (P_{ICG}) detected by the ICG method is $(A + C)/N$.

As significant differences in the numbers of nodes identified by each method would have implications regarding the safety of ICG as a radiotracer, the null hypothesis is that the two methods identify an equivalent nodes of nodes as being sentinel nodes. Here equivalence is defined as the difference in the proportions of nodes flagged between the ^{99m}Tc and ICG methods falling within an interval $(-\delta, +\delta)$, where δ is taken to be 5%. Formally the null hypothesis for equivalence is:

$$P_{\text{ICG}} - P_{\text{Tc}} < -\delta \text{ and } P_{\text{ICG}} - P_{\text{Tc}} \geq +\delta$$

If the null hypothesis is rejected we may conclude for the hypothesis of equivalence that:

$$\delta < (P_{\text{ICG}} - P_{\text{Tc}}) < \delta$$

The equivalence hypothesis can be transformed into two one-sided hypotheses:

(A)

that the difference between the proportions is beyond the lower equivalence margin: null hypothesis A: $P_{\text{ICG}} - P_{\text{Tc}} < -\delta$, which, if rejected, permits the conclusion $P_{\text{ICG}} - P_{\text{Tc}} \geq -\delta$

(B)

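### Does one fluorescence yes/no item per node leave it open whether a node found only at the gamma sweep counts as an ICG miss?

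*Combined protocol and SAP*

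**What the plan says.** Section 3.0 (Study Design, Methods) sets a fixed order of work in the axilla.

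- First the ICG search: "Fluorescent lymph nodes (ICG positive) will be localized and removed". It has a stopping rule: "Node removal will continue until no residual fluorescence is visible in the axilla".
- Then the Tc reading on what has been taken out: "Excised nodes will be tested for radioactivity using a standard gamma-detecting probe", with counts recorded.
- Last the gamma sweep: "the axillary region will be inspected with the gamma probe to determine if there are any residual radioactive nodes". Residual sentinel nodes are removed.

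Tc status has a numerical rule: "With regard to radioactivity, sentinel nodes are defined as any node with at least 10% of the hottest nodal counts". The data list begins "The following information will be collected for each removed node" and has three items: fluorescence yes/no, counts per minute and pathologic status. The other listed data are at patient or procedure level.

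Section 7.0 (Statistical Considerations, Sample size) says that "the sentinel status of a node will be defined as being flagged as sentinel by either one or both of the ICG" or Tc methods. It counts nodes as A (positive by both), B (Tc only) and C (ICG only). Of the Tc-only nodes it says that they "are an error by omission for the ICG method".

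**The concern.** The fluorescence item applies to every removed node, including those taken at the gamma sweep, and no sentence fixes when it is read. Suppose a node is not seen under fluorescence in the axilla, is found with the probe, and fluoresces once it is exposed or excised. If ICG-positive means found by the ICG search, the node belongs in B. If it means the node took up dye, it belongs in A. A form completed either way would fit the data list, and the three listed items could not show afterwards which was done.

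The primary comparison would be at stake, because it depends on B and C alone. Moving nodes from B to A raises the apparent ICG detection rate. Near the lower equivalence margin that could turn a failed comparison into a conclusion of equivalence.

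**Working it through.** **1. The plan's own power figure.** Inputs from section 7.0: Tc detection 97%, so C/N = 1 − 0.97 = 0.03; discordance 6%, so B/N = 0.06 − 0.03 = 0.03; δ = 0.05; 90% interval (z = 1.645); n = 255 nodes.

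- SE = √[((B+C)/N − d²)/n], with d = (C − B)/N = 0, gives √(0.06/255) = 0.01534.
- Power = 2Φ(0.05/0.01534 − 1.645) − 1 = 2Φ(1.615) − 1 = 2 × 0.9468 − 1 = 89.4%.
- Exact trinomial enumeration with a 90% Wald interval gives 88.2%.
- Simulation with a cluster-robust variance (128 patients, 255 nodes) gives 88.0% with no within-patient correlation, 84.0% at a correlation of 0.1 and 80.3% at 0.2. The correlations are assumed.

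The stated power of more than 80% is reproduced.

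**2. What one reclassified node does.** P_ICG − P_Tc = (A + C)/N − (A + B)/N = (C − B)/N. Moving a node from B to A leaves N and P_Tc unchanged and raises P_ICG by 1/255 = 0.39 points.

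**3. Which cell the stated sequence gives.**

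| Node | ICG status from the sequence | Tc status | Cell |
|---|---|---|---|
| Removed in the ICG search, count at or above the 10% rule | positive | positive | A |
| Removed in the ICG search, count below the rule | positive | negative | C |
| Left when no fluorescence is visible, removed at the gamma sweep as a sentinel node | negative | positive | B |

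Each type of sentinel node that the sequence produces has one cell. The third row matches section 7.0's account of Tc-only nodes. The question arises only if a third-row node later fluoresces and is scored yes despite the sequence.

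**4. Sensitivity if some B nodes were scored as A.** The documents give no share, so a range is assumed. Exact enumeration, n = 255, independent nodes:

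| B and C before reclassification | Share of B moved to A | Chance of concluding equivalence |
|---|---|---|
| 3%, 3% (planning) | 0 | 88.2% |
| 3%, 3% | 25% | 88.3% |
| 3%, 3% | 50% | 82.1% |
| 8%, 3% (lower margin) | 0 | 5.8% |
| 8%, 3% | 10% | 12.0% |
| 8%, 3% | 25% | 29.6% |

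In the extreme case at the planning rates, with every ICG miss reclassified, the normal approximation gives 59.0%. There the effect is to make equivalence harder to conclude.

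**5. Sensitivity on observed counts, with no assumed share.** Interval = (C − B)/255 ± 1.645 × √[B + C − (B − C)²/255]/255.

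- B = 20, C = 8, about the expected counts at the lower margin (0.08 × 255 = 20.4; 0.03 × 255 = 7.65): −8.1 to −1.3 points. Equivalence is first concluded at B = 13 (−4.9 to 1.0), after 7 of the 20 misses (35%) have been moved.
- B = 14, C = 8: −5.4 to 0.7. One node moved gives B = 13, C = 8, and the conclusion changes.
- B = C = 8, about the planning counts (7.65 each): −2.6 to 2.6. With all 8 moved it is 1.3 to 4.9, still inside the margin.

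**The case for a change.** The strongest case for acting is that the reading of section 3.0 is an inference. The yes/no item covers gamma-sweep nodes too, Tc has an explicit count rule while fluorescence has no stated time of reading, and the search step cannot be recovered later if it is not noted at surgery. One sentence and one field would be cheap. The narrow factual point stands: neither the search step nor the reading time is among the listed items, and section 7.0 does not mention a gamma-sweep node that later fluoresces.

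The consequence is harder to sustain, for four reasons.

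- The alternative scoring needs a node that was not visibly fluorescent in the axilla, was found by the probe, fluoresced once out and was then entered as ICG-positive against the sequence. The documents give no sign of how often this happens, if at all.
- The rise from 6% to 30% is an error only if ICG-positive means found by the search. If it means dye uptake, moving a quarter of 8% leaves B = 0.08 × 0.75 = 6% and a true difference of 3% − 6% = −3 points. That lies inside the margin, and 30% is then ordinary power.
- Tc status is not open in the same way, because counts and the 10% rule fix it. Reporting a second, search-based comparison would be one-sided: this sequence can show ICG search misses but cannot show Tc search misses among nodes already removed under fluorescence.
- The data form is not in the public documents, so the short list in section 3.0 does not show that the removal step goes unrecorded.

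The one-node example at B = 14, C = 8 lies on the decision boundary, where any threshold rule can turn on a single node.

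**Conclusion.** The plan leaves a detail unstated, and an analyst following its text would fill it correctly: nodes found only at the gamma sweep are ICG-negative and go to cell B. The procedure and the definition of an ICG omission both point that way, so the primary comparison is sound and no change to the plan is called for.

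The size supports this. At the planning rates, reclassifying up to half of the ICG misses keeps the chance of concluding equivalence at 82% or more. At the expected planning counts (B = C = 8), no amount of reclassification alters the conclusion. Material effects need a true difference near the margin, or nearly all misses reclassified, together with scoring that departs from the stated sequence. These figures assume independent nodes, n = 255, a Wald interval and reclassification shares that the documents do not supply. Within-patient correlation would lower the power figures. An explicit sentence would record the convention but would not change the planned analysis.

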4.0 REGISTRATION

All patients enrolled on study will be entered into the Oncore database.

5.0 ADVERSE EVENTS AND REPORTING REQUIREMENTS

Adverse Events and Data Monitoring Committee (DMC):

Although we do not anticipate any adverse events, should any unexpected event occur, we will report the event in a timely manner per IRB policy. A DMC will not be used during this study.

6.0 DATA REPORTING/REGULATORY CONSIDERATIONS

Quality Control and Quality Assurance:

The study coordinator will be responsible to keeping data confidentially documented and reported in compliance with HIPAA and any other applicable regulatory requirements. The data will be kept for approximately 2 years after study completion, and will be accessible only to study staff.

Ethical Considerations:

This study will be conducted according to US and international standards of Good Clinical Practice for all studies. Applicable government regulations and Cleveland Clinic research policies and procedures will also be followed.

This protocol and any amendments will be submitted to the Cleveland Clinic Institutional Review Board (IRB) for formal approval to conduct the study. The decision of the IRB concerning the conduct of the study will be made in writing to the investigator.

7.0 STATISTICAL CONSIDERATIONS

Sample size:

The study will be designed to determine whether ICG based axillary sentinel lymph node biopsy yields a similar number of nodes as ^{99m}Tc sulfur colloid lymph node biopsy. While SLN identification using ^{99m}Tc sulfur colloid is a common technique, neither of the two methods used in this study can be assumed to identify the “correct” set of nodes as sentinel. Therefore, for the purposes of this study, the sentinel status of a node will be defined as being flagged as sentinel by either one or both of the ICG or ^{99m}Tc methods. By this definition, sentinel nodes identified by ^{99m}Tc but not ICG are an error by omission for the ICG method and nodes flagged by ICG but not ^{99m}Tc are an error by the ^{99m}Tc method.

Let A be the number of Tc-positive and ICG-positive SNs detected, B be the number of Tc-positive and ICG-negative SNs detected, and C be the number of Tc-negative and ICG-positive SNs detected. The total number (N) of SNs detected is therefore $N = (A + B + C)$; the proportion of SNs (P_{Tc}) detected by the Tc method is $(A + B)/N$; and the proportion of SNs (P_{ICG}) detected by the ICG method is $(A + C)/N$.

As significant differences in the numbers of nodes identified by each method would have implications regarding the safety of ICG as a radiotracer, the null hypothesis is that the two methods identify an equivalent nodes of nodes as being sentinel nodes. Here equivalence is defined as the difference in the proportions of nodes flagged between the ^{99m}Tc and ICG methods falling within an interval $(-\delta, +\delta)$, where δ is taken to be 5%. Formally the null hypothesis for equivalence is:

$$P_{\text{ICG}} - P_{\text{Tc}} < -\delta \text{ and } P_{\text{ICG}} - P_{\text{Tc}} \geq +\delta$$

If the null hypothesis is rejected we may conclude for the hypothesis of equivalence that:

$$\delta < (P_{\text{ICG}} - P_{\text{Tc}}) < \delta$$

The equivalence hypothesis can be transformed into two one-sided hypotheses:

(A)

that the difference between the proportions is beyond the lower equivalence margin: null hypothesis A: $P_{\text{ICG}} - P_{\text{Tc}} < -\delta$, which, if rejected, permits the conclusion $P_{\text{ICG}} - P_{\text{Tc}} \geq -\delta$

(B)

that the difference between the proportions is greater than the upper equivalence margin: null hypothesis B: $P_{\text{ICG}} - P_{\text{Tc}} \geq +\delta$ which, if rejected, permits the conclusion $P_{\text{ICG}} - P_{\text{Tc}} \leq +\delta$.

Hypotheses A and B will be tested by comparing a two-sided 90% confidence interval (CI) for the difference in the proportions of SNs flagged by the two methods, with the 5% equivalence region ($-\delta$, $+\delta$). Tests for equivalence will be based on the methods for analyzing clustered paired binary data described in Obuchowski(13). To conclude for equivalence the 90% CI needs to be contained entirely within the defined equivalence region, which is equivalent to both null hypotheses (A) and (B) being rejected.

To estimate the number of SNs that will need to be examined, we assumed a detection rate $(A + B)/N$ of 97% for the Tc method, a discordance rate between the two methods $(B + C)/N$ of 6%, and set δ at 5%. We found through simulation that 255 SNs will give adequate power (>80%) to demonstrate equivalence between the two methods, with a type I error (α) rate of 5%. This is estimated to require ~130 patients as the average SN yield is expected to be approximately 2 per patient.

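### Does the misworded null hypothesis in the equivalence test put the trial's conclusion at risk?

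*Combined protocol and SAP*

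**What the plan says.** All the relevant text is in section 7.0, Statistical Considerations, of the combined protocol and SAP. In order, it states:

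- **Prose null:** "the null hypothesis is that the two methods identify an equivalent nodes of nodes as being sentinel nodes".
- **Equivalence region:** a difference in proportions within (-δ, +δ), with δ set at 5%.
- **Displayed null:** "P_{\text{ICG}} - P_{\text{Tc}} < -\delta \text{ and } P_{\text{ICG}} - P_{\text{Tc}} \geq +\delta".
- **Meaning of rejection:** "If the null hypothesis is rejected we may conclude for the hypothesis of equivalence that", followed by "\delta < (P_{\text{ICG}} - P_{\text{Tc}}) < \delta".
- **One-sided nulls:** A, that the difference is below -δ; and B, that it is at or above +δ. Each is given with the conclusion that its rejection permits.
- **Decision rule:** "To conclude for equivalence the 90% CI needs to be contained entirely within the defined equivalence region". The section adds that meeting this rule amounts to rejecting A and B together.
- **Sample size:** 255 sentinel nodes for more than 80% power to demonstrate equivalence at a 5% type I error rate, assuming 97% detection by Tc and 6% discordance.

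**The concern.** Read alone, the first sentence reverses the test. If equivalence were the null, rejecting it would show that the methods differ, and a small or imprecise study would tend to leave it standing. The 5% error rate would then protect against wrongly declaring a difference, when the risk that matters is wrongly declaring equivalence. The displayed formula does not repair this, because taken literally it describes an empty set, so there is nothing to reject and no error rate to define. The following line then says that rejection supports equivalence, which contradicts the prose. This is the study's only formal hypothesis, so an ambiguity about which error is controlled, or about how an inconclusive result is to be read, would be serious if it reached the analysis.

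**Working it through.** **1. Logic of the statements.** Write d = P_ICG - P_Tc and δ = 0.05.

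| Statement in section 7.0 | Set of d | Direction |
|---|---|---|
| Prose null | within ±δ | equivalence is the null |
| Displayed null, as printed | d < -0.05 and d ≥ +0.05 | empty |
| Displayed null, read with *or* | d < -0.05 or d ≥ +0.05 | non-equivalence is the null |
| Sentence on rejection | rejection gives equivalence | non-equivalence is the null |
| Null A | d < -0.05 | non-equivalence, low side |
| Null B | d ≥ +0.05 | non-equivalence, high side |
| 90% interval rule | conclude only if wholly inside ±0.05 | non-equivalence is the null |

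On a grid of 2001 values of d from -1 to 1 in steps of 0.001, none satisfies the printed *and* and 1901 satisfy *or*. The remaining 2001 - 1901 = 100 values run from -0.050 to +0.049. The strict alternative -0.05 < d < +0.05 holds 99 of them, so the two differ only at the boundary point -0.05.

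The likely origin of the *and* is easy to see. Equivalence requires A to be rejected *and* B to be rejected, which is the same as rejecting (A *or* B). The connective belongs to the rejections and was carried into the null.

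**2. Direction implied by the sample size.** Inputs from section 7.0: Tc detection 97%, discordance 6%, δ = 5%, 255 nodes, α = 5% per side (two-sided 90% interval).

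- Nodes missed by Tc: C/N = 1 - 0.97 = 0.03.
- Nodes missed by ICG: B/N = 0.06 - 0.03 = 0.03.
- Assumed true difference: d = (C - B)/N = 0.
- Standard error, nodes independent: √(0.06/255) = 0.01534.
- Power of the two one-sided tests: 2Φ(0.05/0.01534 - 1.645) - 1 = 0.894.

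Simulation with 130 patients, two independent nodes each and a patient-level robust variance also gives 0.894. Both agree with the stated figure of more than 80%. The calculation assumes a true difference of zero and counts a finding of equivalence as success. If equivalence were the null, rejecting it at d = 0 would be a false positive, not power. The sample size therefore fits only the A-and-B reading.

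**3. Effect of correcting the words.** With the null read as d ≤ -5% or d ≥ +5%, the interval, the margin, α, the 255 nodes and the 89.4% are all the same as before, because they were computed from A and B in the first place.

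**4. Smaller slips.** Rejecting B strictly gives d < +δ, whereas the text has d ≤ +δ; this concerns one boundary point and has no practical effect. The lower bound in the displayed conclusion has no minus sign, but the region is printed as (-δ, +δ) elsewhere in the section and the sign may have been lost in text extraction, so it carries no weight.

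**The case for a change.** The strongest case for acting is that the null decides how an inconclusive result is read, and that such a result is plausible at the planned size. Suppose 255 nodes with 11 Tc-only and 4 ICG-only, ignoring clustering. The discordance is 15/255 = 5.9%, and d = (4 - 11)/255 = -2.7 points. The standard error is √((0.0588 - 0.0275²)/255) = 1.51 points, and the 90% interval runs from -5.2 to -0.3. Under the interval rule equivalence is not shown. Someone relying on the prose null could say that equivalence has not been rejected and so stands. The prose sentence also gives a reason for its choice of null, so it is more than a dropped *not*. And the correction would cost a few words.

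What stands is that the sentence and the connective are wrong. What does not stand is the step to opposite conclusions from the same data. The plan gives no test statistic or rejection region for the prose null, and no rule that failing to reject it supports equivalence. To reach the other conclusion, an analyst would have to set aside the explicit interval rule and invent a test. In the example, the plan as written gives one answer: equivalence not shown. Nor is the interval rule the only sound statement: A and B and the sentence on rejection all point the same way, and only the prose sentence points the other.

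**Conclusion.** The drafting errors are real but clerical. Section 7.0 contains a complete two one-sided tests procedure with a single decision rule, and an analyst who follows it reaches a properly directed conclusion. The effect of the misworded sentences on the margin, interval, sample size, power and conclusion is nil, and no change to the plan follows.

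This rests on the analysis following hypotheses A and B and the 90% interval rule, which is what the plan says will be done. The 89% power figure assumes independent nodes and a true difference of zero. The plan does not state the within-patient correlation used in its simulation; at 255 nodes power stays at 80% or more up to a design effect of about 1.24. The 5% error rate is nominal for a large-sample interval: simulation at a true difference of +5% with 6% discordance gave about 7.2%. Neither of these depends on how the null is worded.

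### Does testing only the net difference (C − B)/N leave disagreement between the two methods unchecked?

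*Combined protocol and SAP*

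**What the plan says.** Section 2.0 frames equivalence "in terms of the numbers of nodes identified as sentinel by each method being similar". The goal in Section 1.0 and the opening of the sample-size text in Section 7.0 are also about similar numbers.

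Section 7.0 takes as sentinel any node flagged by either method. It sorts nodes into A (both methods), B (radiotracer only) and C (ICG only), with N = A + B + C. It treats neither method as the reference: "sentinel nodes identified by ^{99m}Tc but not ICG are an error by omission for the ICG method", and the reverse case counts against the radiotracer. It then states that "equivalence is defined as the difference in the proportions of nodes flagged between the ^{99m}Tc and ICG methods falling within an interval" of ±5%. The one planned test compares a 90% interval for P_ICG − P_Tc, from a method for clustered paired data, with that interval. The trial is sized on "a discordance rate between the two methods $(B + C)/N$ of 6" percent, with 97% detection by the radiotracer.

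For every removed node, Section 3.0 collects fluorescence, counts and "Pathologic status of node (no metastasis, isolated tumor cells, micrometastasis, macro-metastasis". The visible text plans no separate estimate of B/N, C/N or (B + C)/N, and no analysis of pathology by cell.

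**The concern.** Two methods can flag equal numbers of nodes and still flag different ones. The plan calls both kinds of discordant node errors, yet its only test lets one kind cancel the other. Total discordance appears only as a planning assumption.

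The text around the test also reaches beyond counting. Section 7.0 says that differences in numbers "would have implications regarding the safety of ICG as a radiotracer". Section 1.0 says "Successful completion of this project would support the use of ^{99m}Tc -labeled radiotracer with ICG for LN mapping", and its background says that "The use of ICG in conjunction with a near infrared camera offers many potential advantages over the use of other techniques". A reader could take a pass to mean that the methods are interchangeable node by node, which a net count cannot establish. If discordance were well above 6% but balanced, the headline result might not show it.

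**Working it through.** **Inputs (Section 7.0).** Margin 5 points; two-sided 90% interval (z = 1.645); 255 nodes; radiotracer detection 97%; discordance 6%; about 2 nodes per patient, about 130 patients. The within-patient correlation is not stated.

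**The tested quantity.** P_ICG − P_Tc = (A + C)/N − (A + B)/N = (C − B)/N. At the planning values C/N = 1 − 0.97 = 3% and B/N = 6% − 3% = 3%, so the true difference is 0.

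**The plan's own figure.** With independent nodes, SE = √(0.06/255) = 0.01534. Power = 2Φ(0.05/0.01534 − 1.645) − 1 = 89.4%; exact enumeration gives 88.2%. Power stays at 80% up to a design effect of about 1.24. The stated power above 80% is consistent with these inputs.

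**Does the test respond to discordance?** The half-width is 1.645 × √[(B + C)/N − ((C − B)/N)²]/√N, so (B + C)/N enters it directly. Chance of passing at N = 255 with equal true miss rates and independent nodes:

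| True discordance | Chance of passing |
|---|---|
| 6% | 88% |
| 10% | 63% |
| 12% | 51% |
| 15% | 34% |
| 20% | 13% (simulated) |
| 23% | 5% |

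A clustered simulation (130 patients, 1 + Poisson(1) nodes each, discordance correlation 0 to 0.3, all assumed) gives 63–64% at 10% and 34–35% at 15% when the directions of misses are independent. When all of a patient's misses go one way it gives 35–54% and 9–20%.

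**Largest observed discordance that can pass (independent nodes).**

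| Net imbalance, nodes | Largest B + C | Share of 255 |
|---|---|---|
| 0 | 60 | 23.5% |
| 1 | 51 | 20.0% |
| 2 | 42 | 16.5% |
| 3 | 35 | 13.7% |

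The 60-node case is an exact tie. A split of 31 and 29 fails, because 0.0078 + 0.04996 exceeds 0.05.

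**Are the miss rates available?** N is the union of flagged nodes, so 1 − P_ICG = B/N, 1 − P_Tc = C/N, and 2 − P_ICG − P_Tc = (B + C)/N. Take two results that both pass with difference 0:

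- 8 + 8 discordant nodes: half-width 2.6 points; each proportion = 247/255 = 96.9%; discordance 16/255 = 6.3%.
- 19 + 19 discordant nodes: half-width 4.0 points; each proportion = 236/255 = 92.5%; discordance 38/255 = 14.9%.

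The proportions that form the primary difference already tell these apart. Wilson 90% intervals for discordance, with independent nodes, are 4.2% to 9.3% and 11.6% to 18.9%.

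**What a pathology table could show.** At the planned rates B and C each hold about 0.03 × 255 = 7.65, or 8 nodes, of which only some would be metastatic. The documents give no positivity rate. Such a table would be descriptive only.

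**The case for a change.** The strongest case for a change is that the ceiling on discordance is a by-product of sample size, not a stated limit, and that it can disappear. The plan cites its clustered method without giving the formula. If the variance is built from patient totals, a patient with one radiotracer-only and one ICG-only node adds nothing to the estimate or the variance. Such swaps in 64 of 128 two-node patients would make half of all nodes discordant and still give an interval of (0, 0). Committing in advance to report B/N, C/N and (B + C)/N would also guard against selective emphasis, at the cost of a paragraph and a table from data already collected.

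Much of this is true. The plan sets no explicit limit on discordance, promises no intervals for it, and visibly assigns pathology no analysis. A pass does not prove node-by-node agreement.

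It does not, however, reveal an error in the planned inference. Even in the swap case, the statement that the methods flag similar numbers would be correct, and P_ICG and P_Tc would each be 75%, which shows the disagreement plainly. The safety remark in Section 7.0 refers to differences in numbers, which the test addresses. The Section 1.0 sentence, read literally, describes using the two agents together, so the plan makes no clear replacement claim for the test to fall short of.

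**Conclusion.** No change is needed. The test matches the stated objective, and with the union of flagged nodes as reference and neither method privileged, equal miss rates are what equivalence means here. Followed as written, the plan supports a conclusion of similar numbers of nodes, and that is all the primary result should be said to show.

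Balanced discordance lowers the chance of passing from 88% at 6% to 34% at 15% and 13% at 20%, with an absolute ceiling of 60 of 255 nodes. These figures assume independent nodes and equal true miss rates. The penalty is stronger if a patient's misses run in one direction, and weakens or vanishes if opposite misses fall in the same patient.

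Both miss rates are by-products of the primary analysis. Reporting them and total discordance with patient-clustered intervals, alongside a descriptive table of metastatic nodes by cell, is a sensible choice for the analyst. It would leave the primary test, the sample size and the planned conclusion as they are.
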